3.5.6 Laboratory Measurements

The following is the list of lab analytes that will be measured throughout the study:

- Chemistry: Sodium, Potassium, Chloride, Total protein, Albumin, Calcium, Magnesium, Phosphorus, Bicarbonate, Glucose, BUN, Creatinine, Total serum Bilirubin, Uric acid, Alkaline phosphatase, AST (SGOT), ALT (SGPT), GGT and CPK.
- Hematology: Red blood cells, Hemoglobin, Hematocrit, Platelets, MCV, MCH, MCHC, White blood cells (WBC), and WBC Differential (percentage and absolute count) (Neutrophils, Eosinophils, Basophils, Lymphocytes and Monocytes)
- Coagulation: aPTT, PT, INR
- Thyroid Panel: TSH, Free T4, and Free T3
- PK: Plasma and CSF ISIS 814907 levels
- CSF Safety Panel (Minimum Requirements): Red blood cells, WBC, Glucose, Protein and Albumin
- Urinalysis: Specific gravity, pH, Protein, Glucose, Ketones, Urobilinogen, Leukocyte esterase, Nitrite, Bilirubin, Blood, Red blood cells, WBC, Epithelial cells, Bacteria, Casts, Crystals, Color and Appearance and P/C ratio
- Additional Safety Tests (plasma): Immunogenicity. (Note: samples have been collected but will not be analyzed.)

In addition:

- Plasma/serum tests measured at screening in Part 1 of the study only: Hepatitis B surface antigen, Hepatitis C antibody, HIV antibody, FSH (women only), Drug/Alcohol Screen, serum folate, serum B12, serum homocysteine, serum uric acid, Treponemal antibody
- CSF tests measured at screening in Part 1 of the study only: CSF homocysteine, folate, B12

Genetic testing is performed at Day -1 in Part 1 of the study will include: APOE, BCHE, IL1RAP, CD33, H1 MAPT haplotype, APP, PSEN1, PSEN2.

Missing WBC differential absolute counts and percentages will be derived as below:

If WBC differential absolute counts are missing, and percentages are available, then absolute counts will be calculated by multiplying the percentage by total WBC count. Conversely, if absolute count is available, and percentage is missing, then percentage will be calculated by dividing absolute count by the total WBC count. If neutrophils counts and percentages are missing, and segmented neutrophil and band neutrophil results are available, then neutrophils will be calculated by adding segmented neutrophils and band neutrophils.

Laboratory tests to ensure patient safety include clinical chemistry panel, hematology panel, coagulation, urinalysis and safety CSF labs (Red blood cells, WBC, Glucose, and Protein), will be summarized by treatment group and each post-baseline visit for the MAD and LTE Periods separately. These safety variables will also be presented as change and percent change from baseline over time after Study Drug administration, as appropriate.

In addition, shift tables will be done for the MAD, LTE, and Active Treatment periods. The shifts (relative to the normal range) from baseline to the minimum and maximum post-baseline values, or shifts to abnormal, as appropriate, for each specific laboratory parameter in the following categories: CSF safety panel, coagulation, hematology, chemistry, and urinalysis (excluding microscopic examination) will be presented. If a subject is missing a baseline value but had a post-baseline value, then the baseline assessment is labeled as "unknown". Likewise, if a subject had a baseline value but had no post-baseline values, then the minimum and maximum are labeled as "unknown". For each parameter, the incidence of shift to low will be summarized using the minimum post-baseline values; the incidence of shift to high will be summarized using the maximum post-baseline values.

Only central laboratory data will be used for the summary tables and figures. Local laboratory data will be provided in the listings only, except for local results for CSF safety tests which will be listed and summarized in tables.

Individual data listings of all laboratory results for MAD Period and MAD+LTE Period will be presented for each subject. All values outside the clinical reference ranges will be flagged in the data listings. The abnormal value is defined as the value below the lower limit or above the upper limit of the clinical reference range. Abnormal laboratory results for the MAD and MAD+LTE Periods will also be displayed in separate listings.

3.5.6.1 Potential clinically significant laboratory abnormalities

For hematology, blood chemistry and urinalysis, the number of subjects with potentially clinically significant (PCS) laboratory abnormalities post-baseline will be summarized for the parameters provided in Table 1 for the MAD, LTE, and Active Treatment analysis periods.

Subjects need to have at least one post-baseline evaluation and a baseline value not potentially clinically significant (including missing) in order to be included in the analysis.

For the LTE and the Active Treatment period analyses, the active treatment period baseline will be used. For early start subjects, PCS abnormalities that occurred in either MAD or LTE will be included in the active treatment period analysis, whereas PCS abnormalities that occurred in the LTE will be included in the LTE analysis. For late start subjects, PCS abnormalities that occurred in the LTE period will be included.

Table 1: Clinical laboratory outlier criteria

| PCS Low | PCS High |
|-----------------------------|--|
| | |
| $<3.0 \times 10^9/L$ | >16 x 10 ⁹ /L |
| <0.8 x 10 ⁹ /L | >12 x 10 ⁹ /L |
| $<1.5 \times 10^9/L$ | $>13.5 \times 10^9/L$ |
| N/A | $>2.5 \times 10^9/L$ |
| N/A | $>1.6 \times 10^9/L$ |
| N/A | $>1.6 \times 10^9/L$ |
| $\leq 3.5 \times 10^{12}/L$ | \geqslant 6.4 x 10 ¹² /L |
| ≤95 g/L | ≥175 g/L |
| ≤115 g/L | ≥190 g/L |
| ≤0.32 L/L | ≥0.54 L/L |
| ≤0.37 L/L | ≥0.60 L/L |
| ≤75 x 10 ⁹ /L | ≥700 x 10 ⁹ /L |
| | |
| N/A | >3 x ULN |
| | >3 x ULN |
| | >3 x ULN |
| | >1.5 x ULN |
| N/A | ≥10.7 mmol/L |
| N/A | ≥176.8 umol/L |
| ≤126 mmol/L | ≥156 mmol/L |
| ≤3 mmol/L | ≥6 mmol/L |
| ≤90 mmol/L | ≥118 mmol/L |
| ≤2.2 mmol/L | ≥9.7 mmol/L |
| ≤2 mmol/L | ≥3 mmol/L |
| ≤0.6 mmol/L | ≥1.7 mmol/L |
| ≤25 g/L | ≥625 g/L |
| ≤45 g/L | ≥100 g/L |
| N/A | ≥1000 IU/L |
| ' | |
| N/A | ≥ 1000 mg/dL; 4+ |
| N/A | ≥ 100 mg/dL; 2+ or higher |
| | <3.0 x 10 ⁹ /L <0.8 x 10 ⁹ /L <1.5 x 10 ⁹ /L N/A N/A N/A N/A ≤3.5 x 10 ¹² /L ≤95 g/L ≤115 g/L ≤0.32 L/L ≤0.37 L/L ≤75 x 10 ⁹ /L N/A N/A N/A N/A N/A N/A N/A N/A Sign N/A N/A |

Note: ULN = upper limit of normal

The clinical laboratory outlier criteria are shown in SI units in this table.

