3.2.3.2 Active treatment period baseline

Active treatment period baseline will be used to analyze the LTE Period and the Active Treatment Period. Active treatment period baseline is the same as the MAD baseline for early start subjects, and for late start subjects is the last non-missing measure collected prior to the first dose of study drug in the LTE except in the instances below:

- o For vital signs (blood pressure [BP] and heart rate [HR]), as the average of the triplicate values collected on Day 1 pre-dose in the LTE. If only one or two assessments are available, the single assessment or average of the two assessments will be used.
- For ECG continuous parameters, as the average of the triplicate values collected immediately prior to first dose in the LTE. For ECG interpretation, baseline will be defined as the worst categorical results of the triplicate results collected immediately prior to first dose in the LTE.
- For C-SSRS suicidal ideation score, as the maximum score collected on Day -1 and Day 1 pre-dose in the LTE.

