3.5.3.2 Incident rates calculation for Active Treatment Period

Incidence rates of AEs which adjust for patient-years on study will be summarized for the Active Treatment Period as indicated previously. The total time on study (patient-years) will be calculated as described in Section 3.5.2. Incidence per 100 patient-years on study will be presented, defined as: [Number of subjects reporting at least one AE during the period / Total time on study (patient-years)] \times 100.

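### In the Active Treatment Period, crude laboratory outlier, shift and liver counts compare early starters followed over MAD plus LTE with late starters followed over LTE only

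*Combined protocol and SAP*

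**What the plan says.** SAP 3.2.1 assigns outliers, hepatotoxicity, shifts and the CSF safety panel to the Active Treatment Period, next to adverse event rates.

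- **Outliers (SAP 3.5.6.1).** The measure is a patient count: "the number of subjects with potentially clinically significant (PCS) laboratory abnormalities post-baseline will be summarized". The entry condition is light: "Subjects need to have at least one post-baseline evaluation and a baseline value not potentially clinically significant".
- **Shifts (SAP 3.5.6).** "shift tables will be done for the MAD, LTE, and Active Treatment periods". They use the worst value, for example "the incidence of shift to low will be summarized using the minimum post-baseline values".
- **Liver (SAP 3.5.6.2).** Patients are counted if the criterion is met at any time after baseline in the analysis period.
- **Windows (SAP 3.5.6.1).** Early starters contribute both parts: "For early start subjects, PCS abnormalities that occurred in either MAD or LTE will be included in the active treatment period analysis". For the others: "For late start subjects, PCS abnormalities that occurred in the LTE period will be included".
- **Baseline (SAP 3.2.3.2).** "Active treatment period baseline is the same as the MAD baseline for early start subjects", so every later MAD and LTE result of an early starter is post-baseline. Late starters are referred to the last value before their first LTE dose.
- **Adverse events (SAP 3.5.3.2).** "Incidence rates of AEs which adjust for patient-years on study will be summarized for the Active Treatment Period". No comparable adjustment is given for the laboratory tables.

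Table B3 of the SAP appendix sets the Early Start and Late Start columns side by side.

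**The concern.** The chance of at least one value beyond a limit rises with the number of values examined. If one column has more tests per patient than its neighbour, its ever-abnormal proportion is higher even when the drug does nothing. Safety is the primary objective, and a reader of the Active Treatment table may take a higher early-start proportion as an effect of earlier or longer exposure. The SAP recognises unequal follow-up in this period for adverse events but not for the laboratory outputs.

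**Working it through.** The plan gives no outlier rate or evaluation count for these tables, so there is no figure to reproduce.

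**1. Scheduled post-baseline evaluations, patients completing both parts (protocol Appendix A.1 to A.4)**

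Chemistry, hematology and urinalysis:
- Early A/B: MAD Days 28, 56, 84, 113, 141, 169, 253 (7); LTE Registration and Day -1 (2); LTE Days 84, 168, 252, 336, 421, 449 (6). Total 15, or 13 if the two samples before the first LTE dose are not counted.
- Early C/D: 8 in MAD (Day 197 is added, and Day 253 is also LTE Day -1, counted once) plus 6 in LTE. Total 14.
- Late: LTE Days 84, 168, 252, 336, 421, 449. Total 6.
- Ratios: 15/6 = 2.50 (13/6 = 2.17) and 14/6 = 2.33.

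CSF safety samples:
- Early A to C: 5 in MAD plus 6 in LTE (pre-dose Day 1 included) = 11. Early D: 3 + 6 = 9. Late: 5, because Day 1 is the baseline.
- Ratios: 11/5 = 2.2 and 9/5 = 1.8.

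**2. Effect of not rolling over**

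Under SAP 3.2.1, early starters who do not enter the LTE stay in the table, while placebo patients who do not enter it drop out. An early starter with MAD data only has 7 (A/B) or 8 (C/D) chemistry evaluations: 7/6 = 1.17, 8/6 = 1.33. If a fraction f completes the LTE and the rest complete MAD only, the early-start mean exceeds 12 (twice 6) when:
- A/B: 7 + 8f > 12, so f > 0.625.
- C/D: 8 + 6f > 12, so f > 0.667.

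For CSF, an Early D patient with MAD data only has 3 samples, fewer than a late starter's 5.

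**3. Ever-abnormal proportion with no drug effect, independent tests**

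P(at least one) = 1 − (1 − p)^n, where p is the assumed chance of an abnormal result per test.

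| p | n = 14 | n = 6 | Ratio |
|---|---|---|---|
| 0.5% | 6.8% | 3.0% | 2.29 |
| 1% | 13.1% | 5.9% | 2.24 |
| 2% | 24.6% | 11.4% | 2.16 |
| 5% | 51.2% | 26.5% | 1.93 |

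With a beta-binomial for within-patient correlation (p from 1% to 5%), the ratio is 1.65 to 1.79 at correlation 0.1 and about 1.3 at 0.5.

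**4. Shift to low, simulated with no drug effect**

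Assumptions: exchangeable normal values, normal range equal to the central 95%, baseline in range.

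| Correlation between tests | 14 tests | 6 tests | Ratio |
|---|---|---|---|
| 0 | 29.8% | 14.2% | 2.1 |
| 0.5 | 16.5% | 9.4% | 1.8 |
| 0.85 | 6.5% | 4.3% | 1.5 |

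For CSF the range is about 1.5 to 2.0 (11 against 5) and 1.4 to 1.7 (9 against 5).

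**5. Absolute size**

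The planned 3:1 split gives 6, 6, 9 and 12 early starters (33 in all) and at most 7 (A+B+C) and 4 (D) late starters.
- Shifts at correlation 0.5, Early D: 12 × (0.165 − 0.094) = 0.85 patient per parameter and direction.
- Outlier limits, taken as 3 SD (assumed): 0.6 to 1.9% against 0.3 to 0.8%. The excess in Early D is at most 12 × (0.019 − 0.008) = 0.13 patient per parameter.

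**6. Would patient-years be enough?**

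Scheduled time is 253 + 449 = 702 days against 449, a ratio of 1.56, while tests differ 2.33-fold. With independent tests and total follow-up as denominator:
- p = 1%: 13.1%/(702/365.25) = 6.8 against 5.9%/(449/365.25) = 4.8 per 100 patient-years. The ratio from unrounded values is 1.43.
- p = 5%: 26.7 against 21.5, ratio 1.24.

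In the shift simulation, first events per patient-year to first event leave a ratio of about 1.56 at correlation 0, 1.2 at 0.5 and 1.0 at 0.85. The proportion of evaluations that are abnormal has a ratio of about 1.0 throughout.

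**The case against.** The strongest reply is that the SAP already plans better tables for the comparison. Outlier, shift and liver outputs are also produced for the MAD Period, where each dose is set against pooled placebo on nearly the same schedule, and for the LTE Period, where early and late starters share the same post-dose visits. The Active Treatment Period is a cumulative summary of exposure with a Total Active column, and the laboratory sections plan no early-versus-late test in it. This stands and limits the weight of the point. The LTE table is not a perfect substitute, because early starters keep their pre-MAD baseline there and may add samples taken before the first LTE dose.

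The adverse event analogy is also imperfect. Adverse events are recorded continuously, whereas laboratory values exist only at visits, so time is not the natural denominator for them. That affects the choice of remedy, not the imbalance itself.

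A reader might infer that early starters as a group have more than twice as many tests throughout. The documents do not support this. It holds for chemistry and hematology in patients who complete both parts, fails for CSF in Early D (1.8), and is diluted by early starters who do not roll over. The SAP also mentions a 23-week UK follow-up. If that added one or two laboratory visits (an assumption; the UK schedule is not in the documents), the C/D ratio would be 15/7 = 2.14 or 16/8 = 2.00.

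**Conclusion.** The imbalance is real and follows from the SAP text and the visit schedule. For chemistry and hematology in completers its direction, against early starters, does not depend on the assumed rates. Its size does. Crude shift incidence is inflated about 1.5- to 2.1-fold for 14 against 6 tests under the stated range and correlation assumptions, and these test ratios are upper bounds for the group average. For the stricter outlier limits the relative inflation is similar, but the expected excess is a small fraction of a patient per parameter.

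A reader might infer that these tables will show false harm from early treatment or hide a late-start signal. That goes too far: the tables are descriptive, sampling noise in columns of 4 to 12 patients is larger than the expected excess, and a late-start signal would also appear in the LTE table. The randomized MAD comparison is not affected. This is a minor-to-moderate point of presentation, worth correcting because the correction is cheap.

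**What to change.** In SAP 3.5.6, 3.5.6.1 and 3.5.6.2, for the Active Treatment Period only:

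- Show the number of post-baseline evaluations in each column.
- Add the proportion of post-baseline evaluations that are abnormal: potentially clinically significant, out of range, or above each liver threshold.
- Keep the crude patient counts as supportive.
- Refer readers to the LTE Period tables for early-versus-late comparison, noting that early starters keep the pre-MAD baseline there.

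Do not rely on patient-years alone. Early starters are also tested more often per year, and a ratio of roughly 1.2 to 1.5 remains at low to moderate correlation.

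The cost is SAP wording and one more denominator. No new data are needed, and these analyses run only after the final lock (SAP 3.4.3.1). The tables become slightly longer, and a per-evaluation proportion gives more weight to patients with repeated abnormal values, which is why the patient counts should stay beside it.

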9.5 Procedures for Handling Special Situations

9.5.1 Abnormalities of Laboratory Tests

Clinically significant abnormal laboratory test results may, in the opinion of the Investigator, constitute or be associated with an AE. Examples of these include abnormal laboratory results that are associated with symptoms, or require treatment, e.g., bleeding due to thrombocytopenia, tetany due to hypocalcemia, or cardiac arrhythmias due to hyperkalemia. Whenever possible, the underlying diagnosis should be listed in preference to abnormal laboratory values as AEs. Clinically significant abnormalities will be monitored by the Investigator until the parameter returns to its pre-dose value or until agreement is reached between the Investigator and Sponsor Medical Monitor. Laboratory abnormalities deemed not clinically significant (NCS) by the Investigator should not be reported as AEs. Similarly, laboratory abnormalities reported as AEs by the Investigator should not be deemed NCS on the laboratory source document.

The Investigator is responsible for reviewing and signing all laboratory reports. The signed clinical laboratory reports will serve as source documents.

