Appendix D Grading Scale for Adverse Events Relating to Laboratory Abnormalities

Appendix D Grading Scale for Adverse Events Relating to Laboratory Abnormalities

The following grading recommendations for adverse events relating to lab test abnormalities are based upon the Common Terminology Criteria for Adverse Events (CTCAE) Version 4.03, June 2010.

| Adverse Event | Mild | Moderate | Severe |
|--|--|--|---|
| | Hem | atology | |
| aPTT prolonged | >ULN - 1.5 x ULN | >1.5 - 2.5 x ULN | >2.5 x ULN; hemorrhage |
| Eosinophils increased [†] | 650 – 1,500 cell/mm ³ | 1,501 - 5,000 cell/mm ³ | >5,000 cell/mm ³ |
| Fibrinogen decreased | <1.0 - 0.75 x LLN or <25% decrease from baseline | <0.75 - 0.5 x LLN or 25 - <50% decrease from baseline | <0.5 x LLN or ≥50% decrease from baseline |
| Hemoglobin decreased (Anemia) | Hemoglobin (Hgb) <lln -="" 10.0="" dl;
<lln -="" 100="" 6.2="" <lln="" g="" l;="" l<="" mmol="" td="">Hgb <10.0 - 8.0 g/dL; <6.2 - 4.9 mmol/L; <100 - 80g/L	Hgb <8.0 g/dL; <4.9 mmol/L; <80 g/L; transfusion indicated	</lln></lln> | Hgb <10.0 - 8.0 g/dL; <6.2 - 4.9 mmol/L; <100 - 80g/L | Hgb <8.0 g/dL; <4.9 mmol/L; <80 g/L; transfusion indicated |
| Hemoglobin increased | Increase in >0 - 2 g/dL above ULN or above baseline if baseline is above ULN | Increase in >2 - 4 g/dL above ULN or above baseline if baseline is above ULN | Increase in >4 g/dL above ULN or above baseline if baseline is above ULN |
| INR increased | >1 - 1.5 x ULN; >1 - 1.5 times above baseline if on anticoagulation | >1.5 - 2.5 x ULN; >1.5 - 2.5 times above baseline if on anticoagulation | >2.5 x ULN; >2.5 times above baseline if on anticoagulation |
| Lymphocyte count decreased | <lln -="" 800="" mm³;
<lln -="" 0.8="" 109/L</lln></lln> | <800 - 500/mm³; <0.8 - 0.5 x 10 ⁹ /L | <500 /mm³; <0.5 x 10 ⁹ /L |
| Lymphocyte count increased | | >4000/mm³ - 20,000/mm³ | >20,000/mm³ |
| Neutrophil count decreased | <lln -="" 1500="" mm³;
<lln -="" 1.5="" 109 /L</lln></lln> | <1500 - 1000/mm³; <1.5 - 1.0 x 10 ⁹ /L | <1000/mm ³ ; <1.0 x 10 ⁹ /L |
| Platelet count decreased | <lln -="" 75,000="" mm³;
<lln -="" 109 /L</lln></lln> | <75,000 - 50,000/mm³; <75.0 - 50.0 x 10 ⁹ /L | <50,000/mm ³ ; <50.0 x 10 ⁹ /L |
| White blood cell decreased | <lln -="" 3000="" mm³;
<lln -="" 109 /L</lln></lln> | <3000 - 2000/mm³; <3.0 - 2.0 x 10 ⁹ /L | <2000/mm³; <2.0 x 10 ⁹ /L |

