Appendix D Grading Scale for Adverse Events Relating to Laboratory Abnormalities Continued

| Adverse Event | Mild | Moderate | Severe |
|------------------------------|---|--|---|
| Cardiac troponin T increased | Levels above the upper limit of normal and below the level of myocardial infarction as defined by the manufacturer | - | Levels consistent with myocardial infarction as defined by the manufacturer |
| CD4 lymphocytes decreased | <lln -="" 500="" mm³;
<lln -="" 0.5="" 109 /L</lln></lln> | <500 - 200/mm³; <0.5 - 0.2 x 10 ⁹ /L | <200/mm³; <0.2 x 10 ⁹ /L |
| CPK increased* | >ULN - <6 ULN | 6 - 10 x ULN | >10 x ULN |
| Creatinine increased | >1 - 1.5 x baseline; >ULN - 1.5 x ULN | >1.5 - 3.0 x baseline; >1.5 - 3.0 x ULN | >3.0 x baseline; >3.0 x ULN |
| GGT increased | >ULN - 2.5 x ULN | >2.5 - 5.0 x ULN | >5.0 x ULN |
| Hypercalcemia | Corrected serum calcium of >ULN - 11.5 mg/dL; >ULN - 2.9 mmol/L; Ionized calcium >ULN - 1.5 mmol/L | Corrected serum calcium of >11.5 - 12.5 mg/dL; >2.9 - 3.1 mmol/L; lonized calcium >1.5 - 1.6 mmol/L; symptomatic | Corrected serum calcium of >12.5 mg/dL; >3.1 mmol/L; lonized calcium >1.6 mmol/L; hospitalization indicated |
| Hyperglycemia | Fasting glucose value >ULN - 160 mg/dL; Fasting glucose value >ULN - 8.9 mmol/L | Fasting glucose value >160 - 250 mg/dL; Fasting glucose value >8.9 - 13.9 mmol/L | >250 mg/dL; >13.9 mmol/L; hospitalization indicated |
| Hyperkalemia | >ULN - 5.5 mmol/L | >5.5 - 6.0 mmol/L | >6.0; hospitalization indicated |
| Hypermagnesemia | >ULN - 3.0 mg/dL; >ULN - 1.23 mmol/L | - | >3.0 mg/dL; >1.23 mmol/L |
| Hypernatremia | >ULN - 150 mmol/L | >150 - 155 mmol/L | >155 mmol/L; hospitalization indicated |
| Hyperuricemia | >ULN - 10 mg/dL (0.59 mmol/L) without physiologic consequences | - | >ULN - 10 mg/dL (0.59 mmol/L) with physiologic consequences |
| Hypoalbuminemia | <lln -="" 3="" dl;
<lln -="" 30="" g="" l<="" td=""><3 - 2 g/dL; <30 - 20 g/L	<2 g/dL; <20 g/L	</lln></lln> | <3 - 2 g/dL; <30 - 20 g/L | <2 g/dL; <20 g/L |

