3.5.3 Adverse Events

3.5.3.1 MAD Period and LTE Period

The incidence (proportion) of treatment-emergent adverse events (TEAEs) will be summarized for the MAD and LTE Periods separately, and incidence (rates) of TEAEs will be summarized for the Active Treatment period where indicated by *. The Medical Dictionary for Regulatory Activities (MedDRA) version 20.0 will be used. Summaries will be presented by preferred term (PT) and system organ class (SOC), unless otherwise indicated, for:

- Any TEAE* (summarized by PT only and by both SOC and PT)
- TEAEs potentially related to Study Drug. Related is defined as "Related", "Possible", or missing relationship to study drug, as determined by the investigator
- TEAEs potentially related to Lumbar Puncture (LP) procedure. Related is defined as "Related", "Possible", or missing relationship to LP procedure
- Any TEAE by severity*. At each level of subject summarization, a subject is classified according to the highest severity if the subject reported one or more events. TEAEs with missing severity will be categorized as "Missing" for this summary
- TEAEs potentially related to Study Drug by severity
- TEAEs potentially related to LP procedure by severity
- Serious TEAEs* (by PT only and by both SOC and PT)
- Serious TEAEs potentially related to Study Drug*
- Serious TEAEs potentially related to LP procedure*
- TEAEs leading to permanent study drug discontinuation* (by PT only and by both SOC and PT)

The number and proportion of LPs leading to TEAEs will be summarized for the MAD and LTE Periods separately. The severity of AEs and SAEs will be graded based on criteria from the Common Terminology Criteria for Adverse Events (CTCAE) Version 4.03, June 2010. SAEs and non-serious AEs that lead to permanent study drug discontinuation will be listed separately. Non-treatment emergent adverse event will be flagged in the data listing.

An adverse event will be regarded as treatment emergent if it is present prior to receiving the first dose of study drug (MAD: ISIS 814907 or placebo; LTE and Active Treatment Periods: ISIS 814907) and subsequently worsened, or is not present prior to receiving the first dose of

study drug (MAD: ISIS 814907 or placebo; LTE and Active Treatment Periods: ISIS 814907) but subsequently appeared.

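### The SAP's low-sodium outlier limit (126 mmol/L or below) is less sensitive than the protocol's severe grade (below 130 mmol/L), so values of 127 to 129 are left out of the PCS counts

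*Combined protocol and SAP*

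**What the plan says.** For each of the three safety analysis periods (MAD, LTE and Active Treatment), SAP 3.5.6.1 states that "the number of subjects with potentially clinically significant (PCS) laboratory abnormalities post-baseline will be summarized for the parameters provided in Table 1". One chemistry row of that table has the limits "≤126 mmol/L | ≥156 mmol/L". To enter the analysis, a subject needs a post-baseline value and a baseline that is not itself PCS; a missing baseline is allowed.

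Protocol Appendix D states that its "grading recommendations for adverse events relating to lab test abnormalities are based upon the Common Terminology Criteria for Adverse Events (CTCAE) Version 4.03". For low sodium it has a mild grade from below the lower limit of normal down to 130 mmol/L, no moderate grade, and a severe grade below 130 mmol/L. For high sodium, severe is ">155 mmol/L; hospitalization indicated". SAP 3.5.3.1 uses the same standard for events: "The severity of AEs and SAEs will be graded based on criteria from the Common Terminology Criteria for Adverse Events (CTCAE) Version 4.03, June 2010".

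Other outputs also carry sodium. In the shift tables of SAP 3.5.6, "the incidence of shift to low will be summarized using the minimum post-baseline values", judged against the normal range. For listings, "All values outside the clinical reference ranges will be flagged in the data listings". Protocol 9.5.1 limits what becomes an adverse event: "Laboratory abnormalities deemed not clinically significant (NCS) by the Investigator should not be reported as AEs".

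**The concern.** A screen for potential significance would normally be at least as sensitive as the trial's own severe grade. For low sodium the order is reversed: the outlier limit lies further from normal than the severe boundary. Safety and tolerability are the primary objective, and the PCS table is the planned laboratory output that counts patients beyond a numerical limit rather than merely outside the reference range.

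The groups are small. At 3:1 in cohorts of 8, 8, 12 and 16, the active groups have 6, 6, 9 and 12 patients. One uncounted patient would be 1/6 = 17% of the 10 mg or 30 mg group, 1/9 = 11% of the 60 mg group and 1/12 = 8% of the 115 mg group.

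**Working it through.** **Identifying the row.** The row labels of Table 1 are missing from the text available for review, which is not a fault of the plan. Among the chemistry analytes listed in SAP 3.5.6, only sodium fits limits of 126 and 156 mmol/L. The next two rows (3 and 6, then 90 and 118 mmol/L) fit potassium and chloride, in the order of that list.

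**Sodium, low side.** Severe is x < 130 and PCS low is x ≤ 126. Values that are severe but not PCS satisfy 126 < x < 130, which in whole numbers means 127, 128 and 129.

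**Sodium, high side.** Severe is x > 155 and PCS high is x ≥ 156. No whole-number value is classified differently.

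**Other low-side limits with a fixed severe grade in Appendix D** (analytes inferred from units and order):

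| Analyte | SAP PCS low | Appendix D severe | PCS limit relative to severe |
|---|---|---|---|
| Sodium, mmol/L | ≤126 | <130 | less sensitive |
| Potassium, mmol/L | ≤3 | <3.0 | same |
| Glucose, mmol/L | ≤2.2 | <2.2, plus need for assistance | same number |
| Phosphorus, mmol/L | ≤0.6 | <0.6 | same |
| Calcium, mmol/L | ≤2 | <1.75 | more sensitive |
| Albumin, g/L | ≤25 | <20 | more sensitive |
| Platelets, ×10⁹/L | ≤75 | <50 | more sensitive |
| White cells, ×10⁹/L | <3.0 | <2.0 | more sensitive |
| Lymphocytes, ×10⁹/L | <0.8 | <0.5 | more sensitive |
| Neutrophils, ×10⁹/L | <1.5 | <1.0 | more sensitive |
| Hemoglobin, g/L | ≤95 and ≤115 | <80 | more sensitive |

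Sodium is the only row of these where a value can be severe without being PCS.

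**Illustrating the size.** The documents give no sodium distribution, so what follows rests on assumptions.

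- *Share of sub-130 values that fall at 127 to 129.* For a normal distribution rounded to whole numbers, the share is 1 − Φ((126.5 − m)/s) / Φ((129.5 − m)/s). Mean 140 and SD 3 give 98.5%; 139 and 3 give 98.0%; 138 and 4 give 88.0%. For a tail that shrinks by a constant ratio r per mmol/L, the share is 1 − r³: 87.5% at r = 0.5, 65.7% at 0.7 and 48.8% at 0.8.
- *How often any value is below 130.* The same normal models give Φ(−3.5) = 0.02%, Φ(−3.17) = 0.08% and Φ(−2.125) = 1.7% of measurements. With 44 patients and about 14 post-baseline panels each if all complete both parts, there are 44 × 14 = 616 panels. Expected values below 130 are about 0.1, 0.5 and 10. Repeat low values tend to come from the same patient, so the number of patients would be smaller still.

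The conflict between the two limits does not depend on any of these assumptions.

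**The case against.** The strongest reply is that the two scales serve different purposes. Appendix D grades adverse events once they are reported, while Table 1 is a numerical outlier screen that never refers to Appendix D. Nothing in the plan says the screen must contain every severe grade, and it does not always do so. The PCS analysis covers hematology, chemistry and urinalysis, so severe aPTT and INR values have no row. The row that by units is creatinine has a fixed upper limit of 176.8 µmol/L, while Appendix D severe includes more than 3.0 times baseline. A patient with a baseline below 176.8/3 = 58.9 µmol/L can be severe without being PCS (55 rising to 170, for example, is 170/55 = 3.1 times baseline). All of this stands. It rules out the reading that sodium is the only gap in Table 1, or that the SAP breaks a stated rule. It does not explain why one fixed low-side limit alone is less sensitive than severe when sodium's own high side matches.

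The second reply is that the data are shown elsewhere. This is also right. A reader might infer that a patient at 128 mmol/L is reported as having no clinically significant sodium value. The documents do not support that: the patient is simply not counted under this criterion. The value enters the by-visit summaries and, if below the reference range, the shift-to-low tables and flagged listings. If the investigator reports it as an event, it can be graded severe and tabulated by severity. What remains is narrower. The shift tables put 128 in the same cell as a value just under the normal range, and a value judged not clinically significant never becomes an event, so no planned laboratory count picks it out.

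**Conclusion.** The inconsistency is real but limited to one analysis table. Sodium values of 127 to 129 mmol/L are severe in Appendix D and absent from the PCS counts in all three safety analysis periods, and the SAP gives no reason. The conclusion rests on reading the unlabelled row as sodium, which the units, magnitude and row order support.

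The number of patients affected is unknown and may be zero or few. A reader might infer from the 49% to 98% range that most severe low-sodium findings in this trial would be missed. That range is a conditional share under assumed distributions, not an estimate from the documents, and it may apply to a count of zero. No dose-escalation rule or efficacy estimate depends on the limit. The point is still worth correcting, because it concerns an output for the primary objective and the change is small.

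**What to change.** In SAP Table 1, change the sodium PCS-low limit from ≤126 to <130 mmol/L, or keep ≤126 and add a <130 mmol/L row beside it, so that the outlier count captures every value Appendix D grades severe. The high limit needs no change. This is a tabulation threshold and alters no clinical rule.

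Under SAP 3.4.3.1 the MAD period is analysed at the interim, and the LTE and Active Treatment periods after final lock. If the MAD tables have already been produced, report the revised MAD count as supplementary.

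The cost is one number or one row. The low-sodium PCS count may become slightly less favourable. Under the existing baseline rule, any subject with a baseline below 130 mmol/L leaves the denominator for the revised criterion; the number excluded for this reason should be reported.
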